3.11. Safety Assessments

3.11.1. Adverse Events (AE)

All Adverse Events (AE) occurring after signing the informed consent are to be recorded on the AE pages of the case report form (CRF). This includes any new signs, symptoms, injury or illness, including increased severity of previous existing signs, symptoms, injury, or illness. Any medical conditions occurring between completion of the double-blind studies and the screening visit of this study will be considered AE and will be recorded and evaluated for seriousness. The ongoing AE's from EN3835 302/303 studies at the time screening of this study will also be imported.

Adverse Events (AE)

An AE is any unfavorable or unintended change in body structure (signs), body function (symptoms), laboratory result (eg, chemistry, ECG, X-ray, etc.), or worsening of a pre-existing condition associated temporally with the use of the study medication whether or not considered related to the study medication. This would include AEs resulting from concurrent illness, reactions to concurrent medication use, or progression of disease states (excluding the disease under study). A condition present at baseline that worsens after initiation of study treatment will be captured as an AE; the onset date will be the date the event worsened.

Serious Adverse Events (SAEs)

Serious adverse event are those AEs that meets any of the following criteria:

- Results in death

- Life-threatening event
- Results in or prolongs an inpatient hospitalization
- Results in permanent or substantial disability
- Is a congenital anomaly or birth defect
- Any important medical event that may jeopardize the patient or may require medical intervention to prevent one of the outcomes listed above

Adverse Events of Special Interest

AEs such as bruising, ecchymosis, hematomas, and contusions that occur remote to the site of drug administration, or any hypersensitivity reactions, including anaphylaxis, will be recorded as an AE of special interest and reported as an AE or SAE as appropriate.

In addition, local AEs associated with the injection site (whether the site was injected in the double-blind study (EN3835-302/303) or in this open-label study (EN3835-304)), including acute (eg, erythema, bruising, pain, nodules/mass, ulceration, erythema, pruritus, swelling, and/or induration) and/or chronic (eg, skin thickening, fibrosclerosis, peau d’orange changes), cutaneous adverse events, will be recorded.

3.11.2. Clinical Safety Laboratory Tests

Blood and urine samples will be collected for testing the following clinical laboratory parameters during the Screening (Day 71 of double-blind study), Day 180, and during the Retreatment Phase [Screening B and Day 71 (End of Treatment/Early Termination)].

Table 12: Clinical Safety Laboratory Parameters

Hematology	Biochemistry	Urinalysis
Hemoglobin	Glucose	Glucose
Hematocrit	Sodium	Protein
Red blood cell	Potassium	Specific gravity
White blood cell (WBC)	Calcium	pH
Platelets	Chloride	Ketones
WBC Differential	Carbon dioxide (CO ₂)	Bilirubin
	Inorganic phosphate	Urobilinogen
	Blood urea nitrogen (BUN)	Nitrite
	Creatinine	Blood*
	Creatinine clearance	Leukocytes*
	Aspartate transaminase (AST)	
	Alanine transaminase (ALT)	
	Gamma-glutamyl transferase (GGT)	
	Total bilirubin (TBL) (direct bilirubin reflex if elevated)	
	Albumin	
	Alkaline phosphatase (ALP)	
	Uric acid	

*Microscopic examination will be performed if blood or leukocytes are detected by dipstick.

Any clinically significant laboratory abnormality observed, will be considered as an AE or SAE as appropriate.

3.11.2.1. Pregnancy Test

For women of child bearing potential, a serum pregnancy test will be performed at Day 71 of the double-blind studies, the results of which will be transferred to the Screening Visit of this open-label study. Additionally, a serum pregnancy test will be performed at the Screening B visit of any Category I and/or eligible Category II subject for the Treatment phase of the study.

Urine pregnancy tests will be performed at Day 180 for all subjects and during Treatment Visits (Day 1, 22, and 43) for subjects who received retreatment (Category I, eligible Category II subjects). Additional urine pregnancy tests will be performed at the discretion of the Investigator when required.

3.11.3. Vital Signs

Vital signs measurements include: systolic and diastolic blood pressure, respiratory rate, pulse rate, body temperature, height, and body weight.

Vital signs measurements (except height and body weight) will be taken at Screening (Day 71 of double-blind study), Day 180, and during Retreatment Phase [Screening B, Day 1, 22, 43, and 71 (End of Treatment/Early Termination)]. On the day of treatment (Day 1, 22, and 43), vital signs (except body temperature) will be measured up to 4 hours prior to study drug administration and at 15 and 30 minutes after the last injection; body temperature will be measured at 4 hours prior to study drug administration and at 30 minutes after the last injection.

Height and body weight measurements will be taken at Screening (Day 71 of double-blind study) for all subjects. Additionally, body weight will be measured at Day 180 and during treatment visits [Day 22, 43 and 71 (End of Treatment/Early Termination)] before injection.

Any abnormality in vital sign observed, will be considered as an AE or SAE as appropriate.

3.11.4. 12-Lead Electrocardiogram (ECG)

A 12-Lead ECG will be performed during the Screening B Visit if Screening B is performed greater than 12 months of an ECG obtained during the double-blind study. During the ECG measurement, the subject will be in a resting position.

ECG result will be interpreted by the Investigators and graded as:

- Normal
- Abnormal, not clinically significant OR
- Abnormal, clinically significant

Any abnormality in ECG observed, will be considered as an AE or SAE as appropriate.

3.11.5. Physical Examination

A complete physical examination (by body system) will be performed at Screening (Day 71 of double-blind study) for all subjects. If the Screening Visit is performed greater than 14 days after the subject's Day 71 of the double-blind study, then an additional evaluation will be conducted at Screening B during the retreatment phase.

This evaluation will include an examination of general appearance, head, eyes, ears, nose and throat, skin, neck, chest, heart, lungs, breasts, abdomen, back, extremities, skin (excluding cellulite), genitalia, lymph nodes, central nervous system, and musculoskeletal system. The Investigator will assess the physical examination findings as normal or abnormal.

If physical examination findings meet the Investigator’s criteria for clinical significance, then it will be reported as an AE or SAE as appropriate.

3.11.6. Immunogenicity Samples

Immunogenicity variables include anti-AUX-I/anti-AUX-II binding (ie, anti-drug) and neutralizing antibody results. Serum samples will be collected at Screening (Day 71 of double-blind study), Treatment visits (Day 22, 43, and 71), and Observation Visits (Day 360, 540, 720, and 1080/EOS) for all subjects for the determination of serum anti-AUX-I and anti-AUX-II antibody levels.

For Category I subjects and/or eligible Category II subjects receiving retreatment, a subset (based on every other sample from the Treatment Visit 4 upper and lower quartiles of binding antibody titers) of subject samples will be tested for neutralizing antibodies from these visits.

4. STUDY PARAMETERS

4.1. Subject Disposition

Subjects will be considered as completing the study if they complete all the safety assessment visits up to 3 years (1080 days) after completing Day 71 of the double-blind studies (EN3835-302 or EN3835-303). Subjects will be considered as completing the retreatment phase of the study if they complete all the treatment sessions and the Day 71 Visit of the retreatment course (if they are eligible for retreatment).

A subject can discontinue the study prematurely; the discontinuation date and reason of early discontinuation will be recorded in eCRF. If a subject discontinues early from the study, then all EOS procedures will be conducted on the day of discontinuation. If, however, a subject withdraws consent, no EOS procedures and assessments are required (but are encouraged to reduce missing information) except the collection of adverse events (AE) information. Discontinued from the retreatment phase, are the subjects who discontinued the treatment prior to the completion of all the treatment session (unless the investigator assessed the buttock(s) as dimple free) or the Day 71 visit of the retreatment course.

The subjects may screen fail after signing informed consent form (ICF) and prior to Day 180, the reason of screen failure prior to Day 180 will also be recorded in eCRF.

The disposition data will also be evaluated at each time period as:

- Day 71/EOS Phase 3 – Day 180 (M6)
- Day 180 (M6) – Day 360 (M12)
- Day 360 (M12) – Day 540 (M18)
- Day 540 (M18) – Day 720 (M24)
- Day 720 (M24) – Day 1080 (M36)

The subjects will be considered as completing a particular time period if they complete study assessments as per protocol schedule of events. Discontinued subjects are those subjects who discontinued the study prior to the time period.

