The Category II subjects that have not shown at least 1-level composite reduction AND/OR have a buttock that has maintained at least a 2-level composite response (ie, have maintained a successful response), and/or Category I and/or Category II subjects who are eligible for a retreatment course but opted not to receive retreatment will have cellulite assessments at Months 12, 18, 24, and 36 from Day 71 of the double-blind study. If the subject's buttock(s) become eligible for retreatment based on the ratings during an observational visit and if they have not already received a course of retreatment in this study, then they will be offered one course of retreatment for the eligible buttock(s); one course of concurrent treatment for up to two eligible buttocks.

If a treatment period overlaps a scheduled observational visit, the observational visit will be skipped, and the subject will re-enter the observational schedule at the next interval visit. For example, if a subject initiated retreatment on Day 351 (which would then be Treatment Visit 1), the treatment period would proceed for approximately 71 days until Day 421 (Treatment Visit 4) and the Observational Visit at Day 360 would be skipped; the subject's next observational visit would be Day 540.

[figure not shown]

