Marking the dimples and injection sites to be treated within the buttocks		X	X	X	

Table 2: Schedule of Events: Eligible Category I/II Subjects – Treatment Session Assessments (Continued)

Procedures^a	Screening B^b (Day -14 to -1 relative to Tx Visit 1)	Tx Visit 1 Tx Session 1 Day 1	Tx Visit 2 Tx Session 2 Day 22 (±3 days)	Tx Visit 3 Tx Session 3 Day 43 (±3 days)	Tx Visit 4 End of Treatment Day 71 (+5 days)^c
Confirm eligibility of buttocks for retreatment ⁿ	X				
Study drug administration		X	X	X	
Injection site reactions/local tolerability in the buttocks ^o		X	X	X	X
Adverse events	Monitored throughout study				

FOOTNOTES:

- ^a Unscheduled visits may be done as deemed necessary at any time during the study to ensure subject safety; assessments done at unscheduled visits are at the discretion of the investigator. No photographs or cellulite severity assessments will be done at unscheduled visits.
 - ^b After the study drug treatment blind is broken in study EN3835-302/303 and subjects have been classified based on Day 71 composite responses in study EN3835-302/303, Category I and Category II subjects that qualify for treatment may elect to receive one and only one course of EN3835 retreatment (ie, 3 treatment sessions) in up to 2 buttocks. If a subject does not qualify to for treatment at that time, she may undergo another Screening B at a later time, if still eligible for treatment.
 - ^c Upon completion of treatment, subject will be followed at intervals as described in Table 3; if the 71-day treatment period overlaps with an Observation Visit in Table 3 for a subject, that particular Observation visit will be skipped, and the subject will be assessed at the next scheduled Observation Visit in Table 3.
 - ^d Informed consent for Category I and eligible Category II subjects who opt to receive retreatment.
 - ^e Photographs of both left and right buttocks should be taken.
 - ^f Before and after marking dimples and injection sites.
 - ^g Including XIAFLEX as a concomitant medication; the use of the word ‘prior’ refers to the period between the last visit from the previous Phase 3 clinical study through the signing of informed consent in the EN3835-304 study; not applicable to subjects who sign consent for this study on the same day that they complete the EN3835-302/303 study.
 - ^h Before injection.

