7. STATISTICAL ANALYSES

7.1. Subject Disposition

The disposition summary table will include the disposition details of all the rollover subjects from the double-blind studies to this open-label extension study. The disposition data will be summarized by number and percentage of subjects for all the subjects in the 180 Day Observational Period and Open-label Period of the study.

For 180 Day Observational Period and Prior to Day 180 Population, the subject disposition summary table will include following information by treatment arm (CCH 1.68 mg, Placebo, and Overall) in the double-blind studies EN3835-302/303:

- Subjects screened
- Screen failure

- Subjects enrolled
- Completed up to Day 180 period
- Completed Day 180 and informed consent form signed for the 3 Year Observational Period
- Completed Day 180 and then Discontinued prior to Open-label Period
- Discontinued in Day 180 period
 - Reason of discontinuation (including subjects who received placebo in the double-blind studies)
- Subject Populations
 - Day 180 Observational Population
 - TRR Population Before Retreatment

For Open-label Period, the subject disposition summary table will include following information subject category (Category I, Category II, Category III, and Overall)

- Subjects entered Open-label Period
- Subject Populations
 - Open Label Observation Population
 - TRR Population Before Retreatment
 - OLR Population
 - OLNLR Population
 - TRR Population After Retreatment
- Completed the study
- Discontinued the study
 - Reason of discontinuation
- Discontinued during the following time period
 - Start of Open-label Period– Day 360 (M12)
 - Day 360 (M12) – Day 540 (M18)
 - Day 540 (M18) – Day 720 (M24)
 - Day 720 (M24) – Day 1080 (M36)

In addition, time in the study will be summarized descriptively, this will include all Category I, II, and III subjects (see [Table 17](#) for computation of time in study).

A listing of disposition from 180 Day Observational Period and disposition from Open-Label Period who entered the Open-Label Period will be provided separately. In addition, the discontinued subjects from the study and screen failures from study will also be listed.

A listing of subject excluded from different analysis population will be provided.

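### Section 4.1 counts period dropouts by a rule that contradicts 7.1, and its study-completer rule does not exempt a visit that the SAP itself directs to be skipped

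*SAP*

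**What the plan says.** **Study completion (SAP 4.1).** "Subjects will be considered as completing the study if they complete all the safety assessment visits up to 3 years (1080 days", counted from Day 71 of the double-blind study. The sentence has no exemption.

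**Period disposition (SAP 4.1).** "The disposition data will also be evaluated at each time period as" introduces five intervals: Day 71/EOS to 180, 180 to 360, 360 to 540, 540 to 720 and 720 to 1080. Two rules follow. For completion: "The subjects will be considered as completing a particular time period if they complete study assessments as per protocol schedule of events". For dropout: "Discontinued subjects are those subjects who discontinued the study prior to the time period".

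**The disposition tables (SAP 7.1).** The open-label table has rows for subjects who completed the study, subjects who discontinued it (with reasons), and "Discontinued during the following time period", the last broken down to Day 720 to 1080. The table up to Day 180 has its own row for subjects who discontinued in that period.

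**The skip rule.** Section 3.1.2: "If a treatment period overlaps a scheduled observational visit, the observational visit will be skipped". Table 2 footnote c repeats it inside the schedule of events: "that particular Observation visit will be skipped, and the subject will be assessed at the next scheduled Observation Visit in Table 3". Section 3.1.2 also lists Months 12, 18, 24 and 36 as the visits at which retreated subjects have safety assessed.

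**The concern.** There are two conflicts. First, leaving before a period and leaving during it are different events, and 4.1 and 7.1 each use one of them for the same breakdown. Section 4.1 holds the parameter definitions, so a programmer could reasonably take the rule from there.

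Second, a subject who follows the plan exactly can be told not to attend a visit that the study-completer rule requires of her. She has not discontinued either, and the study-status rows in 7.1 offer only those two outcomes.

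Long-term safety is a primary objective of this study. Completion and loss by period are what a reader uses to judge how complete the 3-year observation is, so these counts should have one meaning.

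**Working it through.** **Step 1: reproduce the SAP's skipped-visit example.** Section 3.1.2 starts a course on Day 351 and lets it run about 71 days. End = 351 + 71 − 1 = Day 421. Day 360 lies between 351 and 421, so it is skipped, and the next visit is Day 540. This matches the SAP.

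**Step 2: classify that subject.** She attends every visit she is asked to attend, through Day 1080.
- Study completer under 4.1: requires all safety assessment visits. She has no Month 12 visit, so read literally the answer is no.
- Discontinued: she reached Day 1080, so no.
- Period completer under 4.1: requires assessments according to the schedule of events. Table 2 footnote c puts the skip in that schedule, so yes. The period-completer rule is not affected.

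**Step 3: which starts cause a skip?** On nominal days, a course starting on day *s* overlaps visit day *v* if *s* ≤ *v* ≤ *s* + 70. The start days are 290–360, 470–540, 650–720 and 1010–1080. With the +5 days allowed at Treatment Visit 4, the lower limits become 285, 465, 645 and 1005.

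Now suppose a course follows promptly after the visit that triggers it. Confirmation is at 14 ± 5 days, and Screening B is 14 to 1 days before the first injection. Assume Screening B is done no later than the confirmation visit. Then latest start = visit day + window + 19 + 14, and latest end = start + 70 + 5.

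| Triggering visit | Latest start | Latest end | Next visit window opens |
|---|---|---|---|
| Day 180 (±14) | 180 + 14 + 33 = 227 | 302 | 330 |
| Day 360 (±30) | 360 + 30 + 33 = 423 | 498 | 510 |
| Day 540 (±30) | 540 + 30 + 33 = 603 | 678 | 690 |
| Day 720 (±30) | 720 + 30 + 33 = 783 | 858 | 1050 |

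Every prompt course ends before the next visit window opens, so a skip needs a later start. Later starts are possible. Table 1 footnotes e and l allow unblinding and category assignment after Day 180, Table 2 footnote b allows a repeat Screening B, and the Day 351 example is one. The SAP gives no figures on how often this happens.

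**Step 4: place five dropouts under each rule.**

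| Dropout day | 7.1 (during) | 4.1 (prior to), literal |
|---|---|---|
| 100 | 71/EOS–180 | 180–360 and each later period |
| 250 | 180–360 | 360–540 and each later period |
| 400 | 360–540 | 540–720 and 720–1080 |
| 600 | 540–720 | 720–1080 |
| 900 | 720–1080 | none |

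Under 7.1 each dropout falls in exactly one period. Under 4.1 the first period is always empty, earlier dropouts are counted repeatedly, and the last interval's dropouts have no row.

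**The case against.** **On dropout.** Section 7.1 specifies the table, and it uses the sensible rule. The eCRF records the discontinuation date, so each dropout can be placed correctly. The 4.1 sentence directly follows the definition of completing a period and may be a shortened form of *prior to completing* it. A reader might infer that the planned table hides final-year losses. The SAP does not support that. The table is wrong only if programmed from 4.1, and even then the overall discontinued row, time in study and the listing of discontinued subjects still show those losses. What stands is that two sections define one quantity differently. Taking *prior to* as *before the end of* gives a cumulative count, which also does not match 7.1.

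**On completion.** All safety visits can be taken to mean all visits scheduled for that subject, and a retreated subject has safety assessments at her treatment visits. That reading is reasonable but unstated. Where 4.1 wants a by-design exception it writes one: a subject whose buttocks are judged free of dimples is not counted as discontinued from retreatment. The skip rule has no such clause.

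**On size.** A reader might infer that 70/180 = 39% of courses in a 6-month interval, and 70/360 = 19% in the last, cause a skip. Those figures assume starts spread evenly over the interval. The SAP does not support this, because eligibility is tied to ratings at visits and step 3 shows that prompt courses skip none.

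**On bias.** A reader might also infer that completion is distorted between retreated and not retreated subjects. Section 7.1 plans no such comparison, since its columns are Categories I, II, III and Overall. Read literally, the rule also makes a non-completer of any subject, in any category, who misses a safety visit.

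**Conclusion.** Section 4.1 is wrong as written on both points, and the consequence is modest.

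- **Period dropout:** 4.1 contradicts 7.1. If 4.1 is programmed literally, the first period row is empty, earlier losses recur in later rows, and the Day 720 to 1080 losses are absent from the period rows. They remain in the overall discontinued row.
- **Study completion:** an exemption is missing. Read literally, a compliant subject with a visit skipped by design has no final status. This applies at study level only.
- **Size:** the number of subjects cannot be computed, because the SAP gives neither retreatment start times nor a dropout rate. It may be near zero if courses start soon after a visit.
- **Reach:** no analysis population in Table 16 uses completer status, and the reduction-of-response denominators in 7.6.2 and 7.6.3 do not either. The effect is limited to descriptive disposition counts.

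**What to change.** Make two wording changes in section 4.1:

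1. In the period-dropout sentence, replace *prior to* with *during*, so that it matches 7.1.
2. After the study-completer sentence, add that an observation visit skipped under the retreatment-overlap rule (section 3.1.2 and Table 2 footnote c) does not count against study completion.

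Leave the rest of the completer definition unchanged. Redefining a completer as anyone who attends Day 1080 would also admit subjects who missed earlier visits for no planned reason, which is looser than the problem needs. The period-completer rule needs no edit. The cost is two sentences and no new data; the same rules should be used in the disposition programming.

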4.2. Protocol Deviations

Potential deviations will be identified prior to database lock. Protocol deviations will be derived from the eCRF data, electronic vendor data and will be obtained from the clinical monitoring reports. All deviations from these sources will be reconciled and duplicate deviations will be removed.

Possible deviations include, but are not restricted to the following deviation types:

- Ineligible subject/study entry criteria not satisfied
- Informed consent not completed correctly
- Non-compliance with study treatment
- Prohibited medications/procedure
- Visit/procedure missing or out of window

